4.7 Treatment Compliance

All subjects within the safety population will be included in the data analysis.

4.7.1 Variables

Treatment exposure will be characterized by the following variables:

- the duration of study exposure that corresponds to the period from the date of the first dose of study drug to either the date of last study visit (Week 52) for the subjects who completed the study or the date of discontinuation for subjects who discontinued during the study,
- the duration of treatment exposure in days and in subject-years including the duration of dose hold in days for the response assessment/dose hold period (subject-years is calculated by adding the number of subjects in the group and multiplying that number by the years that subjects were on treatment),
- the frequency of treatment exposure determined by the number of injections received,
- the actual amount/dose in mg received by the subjects as well as the percentage of the scheduled dose that was actually received,

Treatment compliance will also be described with:

- the number and proportion of subjects receiving the complete dose as scheduled,
- the number and proportion of subjects that are compliant and non-compliant in each treatment group.

For the induction and maintenance/escalation periods, the duration of treatment exposure is the difference in days between the date of last study visit in the considered treatment period unless subjects have discontinued during this period and the date/time of the first dose of study drug in the same period.

Exposure $_{[\text{period } x]} = \text{last study visit date }_{[\text{period } x]} - 1^{\text{st}} \text{ study drug dose date/time }_{[\text{period } x]}$.

For subjects who have discontinued from placebo at or prior to the last visit of the induction period, the duration of exposure will be the sum of the number of days between the date/time of the first dose and the date of treatment discontinuation.

For subjects who have discontinued from M1095/Secukinumab treatment at or prior to the last visit of the induction or maintenance/escalation periods, the duration of exposure will be the sum of the number of days between the date/time of the first dose in the considered period and the date of the last dose before discontinuation and 56 days that correspond to the longest period of washout for M1095/Secukinumab. If the study discontinuation occurred within the 56 days after the last dose received, the duration of exposure will be defined as the difference in days between the date of study discontinuation and the date of first dose of study drug.

Exposure $_{[\text{period } x]} = \text{last dose date/time }_{[\text{period } x]} - 1^{\text{st}} \text{ study drug dose date/time }_{[\text{period } x]} + 56 \text{ days}$.

The treatment exposure of response assessment/dose hold period will be described by several variables:

- the number of subjects who have dose of study drug being withheld at Week 24,
- the duration in days of the dose being withheld during the period i.e. the difference in days between the date of the visit at Week 24 and the date/time of M1095 re-commencement,
- the total duration in days of the dose being withheld since the last dose of M1095 i.e. the difference in days between the date of the last dose of study drug before dose of Week 24 being withheld i.e. at Week 20 and the date/time of M1095 re-commencement (see Table 4.12).

The duration of exposure to M1095/secukinumab treatment overall during the combined induction, maintenance/escalation and response assessment/dose hold periods be calculated as follows:

Secukinumab: Exposure $_{[\text{overall}]} = \text{date/time of last dose} - \text{date/time of } 1^{\text{st}} \text{ dose} + 56 \text{ days}$.

M1095: Exposure $_{[\text{overall}]} = \text{date/time of last dose} - \text{date/time of } 1^{\text{st}} \text{ dose} - d_1 + 56 \text{ days}$.

with the date/time of the first dose as described in Table 4.12 for the different treatment groups and subtracting the dose hold duration for the overall period while considering the 5 half lives of the M1095 treatment (d_1) as explained in Table 4.12. This duration will also be expressed in subject-years by adding the amount of times in days that subjects spent on treatment for all subjects divided by the total number of days in a year i.e. 365.25.

A subject being administered the complete dose at a given visit is a subject who received the planned number of injections and the planned dosage in mg per injection. A subject being administered the complete dose overall is a subject who received the cumulative number of injections and the cumulative dosage in mg as planned.

A subject will be considered overall compliant for each study period or overall if this subject is missing no more than 20% of the planned treatment and not missing two or more consecutive planned dosing occasions of the considered period or overall. Although subjects will receive two injections at each visit, the two injections at the same visit will be regarded

as a single dosing occasion. If a subject misses two injections at a visit, this subject will be reported as missing the dosing occasion at this visit.

Table 4.12: First M1095 Dose and Calculation of Dose Hold Duration Depending on Treatment Group

Actual Treatment Group	First Dose	Total Dose Hold Duration (d) since last dose of study drug (in days)	Dose Hold Duration for Overall Period (d ₁) (in days) If d-56 < 0, d ₁ = 0
(1) – Placebo at Week 0, 1, 2, 3, 4, 6, 8 (and (1.i) M1095 120 mg at Week 12, 14, 16, 20 and dose hold from Week 24)	Week 12	d = M1095 Restart – Week 20*	d ₁ = d – 56
(1.j) M1095 120 mg at Week 12, 14, 16 and Q4W	Week 12	N/A	d ₁ = 0
(2) - M1095 30 mg at Week 0, 2, 4, 8 (and (2b) M1095 120 mg Q4W if escalation at Week 12)	Week 0	N/A	d ₁ = 0
(2a.i) Q4W and dose hold from Week 24)	Week 0	d = M1095 Restart – Week 20*	d ₁ = d – 56
(2a.j) Q4W)	Week 0	N/A	d ₁ = 0
(3) - M1095 60 mg at Week 0, 2, 4, 8 (and (3b) M1095 120 mg Q4W if escalation at Week 12)	Week 0	N/A	d ₁ = 0
(3a.i) Q4W and dose hold from Week 24)	Week 0	d = M1095 Restart – Week 20*	d ₁ = d – 56
(3a.j) Q4W)	Week 0	N/A	d ₁ = 0
(4) - M1095 120 mg at Week 0, 2, 4, 8 (and (4.i) 12 and Q8W and dose hold from Week 24)	Week 0	d = M1095 Restart – Week 20*	d ₁ = d – 56
(4.j) 12 and Q8W	Week 0	N/A	d ₁ = 0
(5) - M1095 120 mg Q2W at Week 0, 2, 4, 6, 8, 10 (5.i) 12 and Q4W and dose hold from Week 24)	Week 0	d = M1095 Restart – Week 20*	d ₁ = d – 56
(5.j) 12 and Q4W	Week 0	N/A	d ₁ = 0
(6) - Secukinumab 300 mg at Week 0, 1, 2, 3, 4, 8 (and 12 and Q4W)	Week 0	N/A	N/A

*If a subject missed the dose of Week 20, the last visit of the maintenance/escalation period when the subjects were injected the study drug will be considered instead of Week 20.

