1.4 Study Design

This is a multi-center, randomized phase 2b study in subjects with moderate to severe chronic plaque-type psoriasis. Approximately 300 subjects will be enrolled at approximately 60 investigator sites in North America and Europe.

At the end of the initial 4-week screening period (Week -4 to Week 0), all eligible subjects will be randomized within strata of prior biologic use (yes/no) and weight (≤ 90 kg/ > 90 kg) in a 1:1:1:1:1:1 ratio with approximately 50 subjects randomized into each of six treatment groups as shown below and in Figure 1.1:

1. Placebo at weeks 0, 1, 2, 3, 4, 6, 8, 10 / M1095 120mg at weeks 12, 14, 16 and Q4W.
2. M1095 (30 mg) at weeks 0, 2, 4, 8, 12 and Q4W.
3. M1095 (60 mg) at weeks 0, 2, 4, 8, 12 and Q4W.
4. M1095 (120 mg) at weeks 0, 2, 4, 8, 12 and Q8W.
5. M1095 (120 mg) at weeks 0, 2, 4, 6, 8, 10, 12 and Q4W.
6. Secukinumab (300 mg) at weeks 0, 1, 2, 3, 4, 8, 12 and Q4W.

After randomization at Week 0, the study will consist of:

- 3 consecutive treatment periods:
 - A: Induction: a 12-week treatment period (Week 0 to Week 12), which is placebo-controlled,
 - B: Maintenance/escalation: a 12-week maintenance/escalation period (Week 12 to Week 24) where all subjects are on active treatment,

C: Response assessment/dose hold: a 24 week response assessment/dose hold period (Week 24 to Week 48) where active treatment is withheld in subjects who have been administered M1095 during the maintenance period and have an IGA score of 0 at the start of this period i.e. at Week 24,

- followed by a final assessment period (Week 48 to Week 52) for safety/efficacy follow-up.

The study will be double-blinded, subject- and investigator- blinded, during all treatment periods up to Week 52 (refer to the unblinding plan for further information about the timepoints when specific teams will be unblinded during the study). Blinding will be maintained prior to Week 52 using masking techniques. Therefore, up to Week 24, subjects randomized to 30 and 60 mg M1095 (Arms 2 and 3) will be administered placebo at Weeks 1, 3, 6, 10 and 14 in order to preserve the blinding. Similarly, subjects randomized to 120 mg M1095 (Arm 4) will receive placebo at Weeks 1, 3, 6, 10, 14 and 16 and subjects randomized to 120 mg M1095 (Arm 5) will receive placebo at Weeks 1, 3 and 14. Subjects randomised to Secukinumab (Arm 6) will receive placebo at Weeks 6, 10 and 14.

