4.7.2 Descriptive Analyses

The duration of study exposure will be summarized. Summary statistics of the duration of treatment exposure in days and in subject-years will be reported by treatment group for the induction, maintenance/escalation and overall periods. The treatment exposure of the response assessment/dose hold period will be described with the number of subjects who have dose withheld and with summary statistics of the duration of the dose being withheld and of the total duration of the dose being withheld since the last dose of M1095.

The frequency of treatment exposure and the amount/dose of treatment will be provided at each visit and overall for each treatment period. The percentage of the scheduled dose will be reported for the induction, maintenance/escalation and overall periods.

All descriptive analyses on treatment compliance will be also summarized for the three treatment periods and for the overall study. The number and proportion of subjects having received the complete dose administered will be presented by each dose administered and overall by treatment group. Proportions of subjects compliant and non-compliant with study drug will be summarized by treatment group.

Data for study drug administration will be listed by treatment group and subject.

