4.9.2.5 Adverse Events

Treatment-Emergent AEs (TEAEs) per treatment period are AEs that emerge while on study treatment during a given treatment period (e.g. induction period), having been absent pre-treatment, or that worsen during the considered period (e.g. induction period) relative to the pre-treatment state i.e. after baseline and on or prior to the date of the last visit of the considered period (e.g. Week 12 for the induction period). On study treatment during a treatment period is defined as the period from the first study treatment administration at the start of period (e.g. Week 0 for the induction period) up to the last visit of the treatment period for subjects who did not discontinue treatment during the considered period (e.g. Week 12 for the induction period) or for subjects who discontinued during the considered period, up to the end of the considered period or up to 8 weeks after the last dose of study treatment, whichever occurs first. TEAEs will be assigned to the actual treatment period to which they are considered treatment-emergent.

When considering the study overall, treatment-Emergent AEs (TEAEs) are AEs that emerge while on study treatment i.e. from the first study treatment administration up to 8 weeks after the last dose of study treatment, having been absent pre-treatment, or that worsen during study treatment relative to the pre-treatment state i.e. after baseline.

If the classification of an AE cannot be clearly established because of missing or incomplete date/time of AE, the AE will be classified as treatment-emergent. No imputation of missing or partial AE start and end dates will be performed.

To determine whether an AE is pre-treatment, on-treatment or post-treatment in case of partial or missing AE dates, the rules below will be followed:

- If the start date is incomplete and either the end date is incomplete or available:
 - if the non-missing part of the start date infers that the AE occurred post-treatment, the AE will be considered as post-treatment.
 - If the partial or complete end date indicates that the AE occurred prior to the first dose of study drug, the AE will be considered as pre-treatment.
 - If the partial start date does not give any evidence as to when the AE occurred during the study, and the end date infers that the AE stopped after the first dose of study drug, the AE will be flagged as on-treatment for all periods for which the first dose of study drug was started before the end of the AE.

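### SAP 4.7.1 does not cut period exposure at the end of the period for M1095 and secukinumab discontinuers, so a subject who stops drug but stays in the study can be credited with more than the 84-day period

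*SAP*

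**What the plan says.** SAP 4.7.1 has three rules for treatment exposure within the induction or maintenance/escalation period.

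- **Completers:** last study visit in the period minus first dose in the period.
- **Placebo discontinuers (induction):** date of treatment discontinuation minus first dose, with nothing added.
- **Active discontinuers**, meaning subjects who have "discontinued from M1095/Secukinumab treatment at or prior to the last visit of the induction or maintenance/escalation periods": last dose minus first dose in the period, plus "56 days that correspond to the longest period of washout for M1095/Secukinumab".

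A limit follows the third rule. "If the study discontinuation occurred within the 56 days after the last dose received", exposure becomes the "difference in days between the date of study discontinuation and the date of first dose of study drug". No sentence limits it to the end of the period.

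SAP 4.7.2 plans descriptive tables in which "the duration of treatment exposure in days and in subject-years will be reported by treatment group for the induction, maintenance/escalation and overall periods". For adverse events in the same periods, SAP 4.9.2.5 counts a discontinuer as on treatment "up to the end of the considered period or up to 8 weeks after the last dose of study treatment, whichever occurs first".

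**The concern.** The rule can give more period exposure to a subject who stopped than to one who continued. Take two Arm 5 subjects with the same induction doses who both attend Week 12. One carries on and is credited with 84 days. The other stops at Week 12, stays in follow-up and is credited with 126. Their induction treatment was identical.

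This is the usual course for someone who stops drug, not a rare one. Protocol 7.1 says that stopping study treatment is not withdrawal from the study. Protocol 8.1.11 plans contacts 28 and 56 days after the last dose and then telephone calls up to Week 52, so the study-discontinuation limit will often not apply.

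At stake is the accuracy of the exposure tables by arm and period. Days after the period are counted as exposure in it, although the period adverse event window excludes them. There is also a timing problem. SAP Table 2.1 lists treatment compliance and/or exposure up to Week 12 for the first interim analysis. For a Week 10 last dose, the credited value depends on whether the subject leaves the study by Day 127 (Day 71 + 56), which Week 12 data cannot settle.

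**Working it through.** **Inputs**

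- Nominal visit days, from the protocol Schedule of Activities: Week 0 = Day 1, Week 4 = Day 29, Week 6 = Day 43, Week 8 = Day 57, Week 10 = Day 71, Week 12 = Day 85, Week 20 = Day 141, Week 24 = Day 169, Week 44 = Day 309, Week 52 = Day 365.
- Period length, from SAP 1.4: "Induction: a 12-week treatment period (Week 0 to Week 12), which is placebo-controlled". That is 85 − 1 = 84 days. Maintenance/escalation is 169 − 85 = 84 days.
- Dosing, from SAP 1.4. Arm 5 is "M1095 (120 mg) at weeks 0, 2, 4, 6, 8, 10, 12 and Q4W", so its last induction dose is at Week 10. Arms 2-4 and 6 have their last active induction dose at Week 8, and their Week 10 injection is masking placebo. In maintenance/escalation every arm has an active dose at Week 20.

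**The SAP's 56 days**

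8 weeks × 7 = 56. Protocol 2.3 gives an M1095 half-life of 11 to 12 days, so five half-lives are 55 to 60 days, which brackets 56. The documents give no secukinumab half-life, so that part cannot be checked.

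**Induction exposure for an active discontinuer who stays in the study at least 56 days after the last dose**

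Formula: (last dose day − 1) + 56.

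| Last dose | Calculation | Days credited | Ended at period end |
|---|---|---|---|
| Week 4 | 28 + 56 | 84 | 84 |
| Week 6 | 42 + 56 | 98 | 84 |
| Week 8 | 56 + 56 | 112 | 84 |
| Week 10 | 70 + 56 | 126 | 84 |

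A completer gets 84. The Week 10 case is 42 days, or 50%, above that: 126 / 365.25 = 0.345 subject-years against 84 / 365.25 = 0.230. The Week 8 case is 28 days, or 33%, above.

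**With the existing limit at study discontinuation**

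- Last dose Week 10, leaves the study 14 days later: 70 + 14 = 84.
- Last dose Week 10, leaves 28 days later: 70 + 28 = 98.
- Last dose Week 10, leaves 55 days later: 70 + 55 = 125.
- Last dose Week 8, leaves 14 days later: 56 + 14 = 70.

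The limit lowers the figure but does not hold it to 84.

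**Maintenance/escalation, last dose Week 20**

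(141 − 85) + 56 = 112 days, against 84 for a completer.

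The limit sentence has a second problem here. It counts from the first dose of study drug and does not say that this means the first dose in the period. Read literally, a subject whose last dose was at Week 20 and who leaves the study on Day 169 is credited with 169 − 1 = 168 days, instead of 169 − 85 = 84.

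**Overall period, as a check**

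For a completer with no dose hold: (309 − 1) + 56 = 364 days, and 365 − 1 = 364. That formula agrees with the Week 52 visit.

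**Effect on an arm mean**

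The documents give no expected share of such subjects, so a share p is assumed here, with all others completing. For Arm 5 with last dose at Week 10, the mean is 84 + 42p. For Arms 2-4 and 6 on active doses, with last dose at Week 8, it is 84 + 28p.

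| p (assumed) | Arm 5 mean | Change | Arms 2-4, 6 mean | Change |
|---|---|---|---|---|
| 2% | 84.8 | +1.0% | 84.6 | +0.7% |
| 5% | 86.1 | +2.5% | 85.4 | +1.7% |
| 10% | 88.2 | +5.0% | 86.8 | +3.3% |
| 20% | 92.4 | +10.0% | 89.6 | +6.7% |

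**The case against.** The best defence is that the 56 days are a stated convention for residual drug, tied to about five half-lives and used in the overall formula as well. A discontinuer has no later treatment period in which those days could appear, and placebo subjects have no drug to wash out, so adding nothing for them is reasonable.

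The placebo point stands: unequal treatment of placebo and active discontinuers is not in itself a defect. The convention is also sound for the overall period. It does not carry over to a single period. A completer also has residual drug at the last visit, and the SAP ends that subject's period exposure there. The SAP also applies the period-end limit to adverse events, so it already treats period end as a boundary.

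Three stronger readings are tempting, and the documents do not support them.

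- **That the added days have no limit at all.** They do: study discontinuation within 56 days of the last dose.
- **That every active discontinuer dosed after Week 4 exceeds 84 days.** The subject must also stay in the study past Day 85. A Week 8 last dose with exit 14 days later gives 70 days.
- **That adverse event rates are diluted.** SAP 4.9.2.5 plans exposure-adjusted incidence for the overall period only. Its period-level tables give numbers and percentages of subjects.

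**Conclusion.** Wrong as written, with a small consequence. The rule gives a reported period exposure longer than the period itself, and two subjects with identical dosing get different values depending only on whether they continue.

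The maximum on nominal visit days is 126 days in induction for Arm 5 and 112 days for Arms 2-4 and 6 on active doses. The latter rises to 126 if the Week 10 masking placebo counts as the last dose, which the definition of study drug in Protocol 6.0 would allow. In maintenance/escalation the maximum is 112 days. Each compares with 84 for a completer, and each requires the subject to stop drug but remain in the study for at least 56 days after the last dose.

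These are single-subject maxima, and a reader might take the 50% excess as the size of the error in a table. It is not: under the assumed shares of 2% to 20%, arm means rise by about 1% to 10%. Only the descriptive induction and maintenance/escalation exposure summaries, in days and subject-years, are affected. Efficacy, the overall exposure figures and the planned adverse event rates are not.

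**What to change.** In SAP 4.7.1, for M1095 and secukinumab discontinuers in the induction or maintenance/escalation period, define period exposure as the earliest of (a) last dose in the considered period plus 56 days, (b) study discontinuation and (c) the end of the considered period, minus the first dose in the considered period. Amend the limit sentence so that its start date is also the first dose in the considered period. Say whether a masking placebo injection counts as the last dose; with the new limit this no longer changes the Week 8 and Week 10 induction cases above for a subject who stays in the study, since both give 84 days.

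Leave the overall-period formula unchanged. The cost is a sentence or two in the SAP and one extra term in the exposure derivation. No new data are needed.
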